	
Title 43USTT1904 CSP Infraorbital Hollows
	
Doc id MA-40833

--	---	-----------------------------------

Effective date: 2021-12-15 20:29

	
sufficient number of subjects in the mITT population used in the assessment of the primary effectiveness endpoint.
 
The study was initially planned to enroll a total sample size of approximately 238 subjects; approximately 204 randomized to treatment with Restylane-L (~102 injected using needle, and ~102 injected using cannula) and approximately 34 randomized to no treatment.
 
Based on information on missing data and the number of remote visits performed at study sites so far, the study is now planned to enroll approximately 329 subjects; approximately 282 will be randomized to treatment with Restylane-L (~146 will be injected using needle, and ~136 will be injected using cannula) and approximately 47 will be randomized to no treatment in order to achieve the required number of mITT subjects in each stratum.
 
Previous data Since the primary endpoint will be based on a new scale, no existing data is available.
 
CCI
 
--	--

Effective

Version: 10.0

Abbreviations and Definitions of Terms

AE	Adverse Event
AESI	Adverse Events of Special Interest
Blinded evaluator	An evaluator responsible for independent evaluation of treatment result(s). The evaluator must not be involved in the treatment of the subject.
CFR	Code of Federal Regulations
Childbearing Potential	A female (including pre-menopausal subjects) capable of becoming pregnant; this includes women on oral, injectable, or mechanical contraception or women whose male partners have been vasectomized or are utilizing mechanical contraceptive devices
CMH test	Cochran-Mantel-Haenszel test
CRO	Contract research organization
CSP	Clinical Study Protocol
CTA	Clinical trial agreement
CTN	Clinical trial number
CV	Curriculum vitae
Device deficiency	Inadequacy of a medical device with respect to its identity, quality, durability, reliability, safety, or performance (includes malfunctions, use errors, and inadequate labelling)
DMP	Data management plan
eCRF	Electronic case report form
EOS	End of Study
ET	Early termination
FDA	United States Food and Drug Administration
FL	Forehead Lines
FSFV	First Subject First Visit, i.e. first subject who signs the informed consent form
FST	Fitzpatrick Skin Type
G	Gauge
GAIS	Global Aesthetic Improvement Scale
GCP	Good clinical practice
GDPR	General Data Protection Regulation

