10.2 Analysis populations

The following populations will be defined:

- **Modified Intention-to-treat (mITT)** Includes all subjects who are randomized and will be analyzed according to the randomization scheme; subjects with a GIHS month 3 assessment via a remote visit will be excluded from the mITT.
- **Intention-to-treat (ITT)** Includes all subjects who are randomized and will be analyzed according to the randomization scheme
- **Per protocol (PP)** Includes all subjects in ITT who complete 3 months after baseline visit without any deviations considered to have substantial impact on the primary effectiveness
- **Safety** Includes all subjects who were treated with *Restylane-L* or randomized to the control group, and will be analyzed according to as-treated principle

The mITT will be used for the primary effectiveness analysis. All secondary effectiveness endpoints will be analyzed based on the ITT population, ^{CCI}

Safety analysis is performed based on the safety population set.

The disposition of subjects will be presented in tables and/or figures as appropriate. The number of screened, treated, completed, and withdrawn subjects will be presented, as well as number of subjects in each analysis population set.

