#### 1.4 Effectiveness endpoints

#### 1.4.1 Primary effectiveness endpoint/estimand

The primary endpoint of the study is the Responder rate based on the Blinded Evaluators' live assessment of the GIHS at 3 months after baseline.

A responder is defined as a subject with at least one-point improvement from baseline, on both sides of the face concurrently.

The primary estimand is then the difference in proportions of GIHS responders at Month 3 in the Restylane-L group versus a No Treatment control group in subjects who are randomized at baseline and did not have a remote month 3 GIHS assessment.

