#### 2.4.3 Primary effectiveness analysis

The primary effectiveness analysis will be done using the mITT Population. To evaluate the effectiveness of Restylane-L versus no-treatment control in the correction of Infraorbital Hollows, the GIHS responder rates (defined in Section 1.3.1) at Month 3 after baseline will be compared using the CMH test stratified by injection tool at the 5% significance level (2-sided).

The null hypothesis will be that there is no relationship between GIHS responder rate and treatment group (i.e. the responder rate is the same in both Restylane-L and no treatment groups). The alternative hypothesis will be that there is a relationship between responder rate and treatment group (i.e. the responder rate is different in the two groups). For a significant result, the two-sided p-value of the comparison of GIHS responder rates between the treated and untreated subjects at Month 3 using the CMH test needs to be smaller than 0.05.

The estimates of the GIHS responder rates in each treatment group will be presented as well as the difference in responder rates (Restylane-L responder rate – No Treatment responder rate). Corresponding 95% CI for the treatment group GIHS responder rates and the difference in responder rates along with the p-value for the difference will also be presented. The normal approximation (Wald) method will be used to calculate the 95% CI for the individual treatment group GIHS responder rates as well as the 95% CI for the difference in responder rates.

Effective date: 2021-12-1713:25

Version: 3.0

Title 43USTT1904 Statistical analysis plan - Tear Trough

Doc id

[figure not shown]
Print date:

MA-42205

2022-08-17 17:26

Effective

Effective

Print date:

[figure not shown]
2022-08-17 17:26

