#### 2.4.4.1 GIHS

Responder rates based on the GIHS determined by the Blinded Evaluator (described in Section 1.3.1) will be analyzed using the CMH test stratified by injection tool. This test will use the ITT Population on the observed cases following the methods described in Section 2.4.3 and will be presented by visit. No correction for multiplicity will be done; p-values (if generated) will only be provided for ease of interpretation of the results.

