#### 2.7 Determination of Sample Size

Due to the public health emergency related to the COVID-19 pandemic during 2020, steps have been taken to ensure patient and practitioner safety in alignment with FDA Guidance dated May 11, 2020 (Guidance on Conduct of Clinical Trials of Medical Products during COVID-19 Public Health Emergency). Most notably, in partnership with clinical sites and the IRB, optional remote assessment procedures for efficacy and safety endpoints has been implemented to ensure safety and respect localized and elective restrictions. Therefore, the sample size has been increased during the conduct of the study to ensure a sufficient number of subjects in the mITT population used in the assessment of the primary effectiveness endpoint.

The study was initially planned to enroll a total sample size of approximately 238 subjects; approximately 204 randomized to treatment with Restylane-L ( $\sim$ 102 injected using needle, and  $\sim$ 102 injected using cannula) and approximately 34 randomized to no treatment.

Based on information on missing data and the number of remote visits performed at study sites so far, the study is now planned to enroll approximately 329 subjects; approximately 282 will be randomized to treatment with Restylane-L (~146 will be injected using needle, and ~136 will be injected using cannula) and approximately 47 will be randomized to no treatment in order to achieve the required number of mITT subjects in each stratum.

2022-08-17 17:26

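### With about 47 controls, the Wald 95% interval for the primary responder-rate difference covers less than 95% and errs mostly in the product's favour; the CMH test is unaffected

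*SAP*

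**What the plan says.** SAP 1.4.1 defines the target: "The primary estimand is then the difference in proportions of GIHS responders at Month 3", Restylane-L against no treatment. SAP 2.4.3 tests it with a two-sided CMH test stratified by injection tool, and success is p < 0.05. For estimation it says "The estimates of the GIHS responder rates in each treatment group will be presented as well as the difference in responder rates". It then fixes the interval method: "The normal approximation (Wald) method will be used to calculate the 95% CI for the individual treatment group GIHS responder rates". The same sentence sets Wald for the interval on the treatment difference too. The visible text gives no small-sample alternative.

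SAP 2.7 plans about 282 treated subjects (146 needle, 136 cannula) and says that "approximately 47 will be randomized to no treatment in order to achieve the required number of mITT subjects in each stratum". The primary analysis uses the mITT set, and under Protocol 10.2 "subjects with a GIHS month 3 assessment via a remote visit will be excluded from the mITT", so fewer than 47 controls may be analysed. Missing Month 3 data are multiply imputed (SAP 2.4.2, with details in Appendix H, which is not visible).

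For the GIHS comparisons at later visits, SAP 2.4.4.1 refers back to SAP 2.4.3: "This test will use the ITT Population on the observed cases following the methods described in" that section. On expected rates, the Protocol synopsis says only "Since the primary endpoint will be based on a new scale, no existing data is available".

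**The concern.** The Wald interval for a difference takes its standard error from the observed rates. With few controls and a control rate well below one half, two errors go together. When the control count happens to be low, the estimated difference is too large, and the estimated control variance is too small. Both push the lower limit up. The interval is therefore too short in just those trials where the estimate flatters the product.

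The extreme case is zero control responders. The control-rate interval is then [0, 0], and the control arm adds no variance to the difference.

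What is at stake is the stated precision of the primary estimand in a study meant to support a US marketing application (Protocol 2.3). The success decision is not at stake.

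**Working it through.** **Inputs from the documents.** Treated n = 146 + 136 = 282 and control n = 47, total 329, a ratio of 6:1 (SAP 2.7). The level is 95%, two-sided (SAP 2.1). The plan gives no figure for the interval beyond its nominal 95%, so there is nothing further to reproduce.

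**Assumed inputs.** True treated rate 60-90% in 5-point steps (7 values) and true control rate 2-40% in 1-point steps (39 values): 7 × 39 = 273 combinations.

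**Formula.** With observed rates a and b, Wald is (a − b) ± 1.96 × √[a(1 − a)/282 + b(1 − b)/47].

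Example, 226/282 v 5/47: a = 0.8014, b = 0.1064, difference 0.6950. The variance terms are 0.000564 (treated) and 0.002023 (control), so SE = √0.002587 = 0.0509. The lower limit is 0.6950 − 1.96 × 0.0509 = 0.595. Controls supply 0.002023/0.002587 = 78% of the variance, so their small number governs the result.

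**Coverage.** For each combination, the exact binomial probabilities of all 283 × 48 possible outcomes were summed over the intervals that contain the true difference. Misses were split by side. Entries are coverage %, with the percentage of trials whose lower limit lies above the truth in brackets (nominal 2.5):

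| Treated rate | Control 5% | 10% | 20% | 30% | 40% |
|---|---|---|---|---|---|
| 60% | 93.3 (5.6) | 93.1 (5.6) | 93.9 (4.5) | 94.1 (3.8) | 94.2 (3.3) |
| 80% | 92.0 (7.2) | 93.0 (6.0) | 93.6 (4.9) | 94.1 (3.9) | 94.2 (3.4) |
| 90% | 90.7 (8.7) | 91.9 (7.1) | 93.5 (5.1) | 94.0 (4.1) | 94.1 (3.5) |

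Over all 273 combinations:
- Coverage is 89.4-94.3% for control rates of 2-20% and 93.2-94.2% for 20-40%. None reaches 95%. The median is 93.7%.
- The lower-side miss is 3.3-10.0% and exceeds the upper-side miss in every combination.
- Five combinations fall below 91%, all at treated 90% with control 2-6% (minimum 89.4% at control 4%). Sixteen fall below 92%.

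**Fewer controls.** If mITT held 240 v 40 (assumed), coverage at treated 80% would be 91.9, 92.0, 93.4, 93.6 and 94.1% for control rates of 5, 10, 20, 30 and 40%. The minimum over the 273 combinations would be 88.1%.

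**Control rate alone, n = 47.** Wald covers 61% at a true rate of 2%, 91% at 5%, 95% at 10%, 91% at 20%, 94% at 30% and 95% at 40%. The chance of zero responders, and so of [0, 0], is 0.95^47 = 9% at a true rate of 5% and 0.90^47 = 0.7% at 10%.

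**Checks on the simplification.** The figures above are unstratified and assume complete data.
- A CMH-weighted Wald interval (146/24 and 136/23) covered 90.4-94.2% for control 2-20% and 93.1-93.9% for 20-40%.
- With 5% and 15% missing completely at random, Beta(0.5, 0.5) imputation by arm, 20 imputations and Rubin pooling (all assumed), coverage was 90.5-94.4% and the lower-side miss 3.4-8.9%.
- The simulated type I error of the CMH test was 3.9-5.0% at the same stratum sizes. The test does not use the Wald variance.

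**Effect on a reported result.** Fall in the lower limit, in percentage points, when Wald is replaced, with 226/282 treated responders:

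| Control responders | 0/47 | 5/47 | 9/47 | 14/47 | 19/47 |
|---|---|---|---|---|---|
| Miettinen-Nurminen | 3.2 | 2.7 | 2.0 | 1.1 | 0.3 |
| Newcombe | 4.4 | 3.0 | 2.1 | 1.2 | 0.3 |

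For 5/47 the lower limits are 59.5 (Wald), 56.8 (Miettinen-Nurminen) and 56.5 (Newcombe).

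**The case against.** - **No decision rests on this interval.** Success is CMH p < 0.05, and no visible text sets a threshold for a confidence limit. A lower limit of 36.5 rather than 35.3 points (226/282 v 14/47, Wald v Newcombe) changes no conclusion that the plan defines. This stands, and it limits the weight of the point.
- **The typical shortfall is small and the rates are assumed.** Of the 273 combinations, 220 cover at least 93%, and the low values come from one corner. The documents cannot show which region applies. This also stands. But no combination reaches 95%, and the direction is the same throughout.
- **The reported interval will be pooled over imputations by a rule that is not visible**, and Wald's estimate-plus-or-minus-SE form suits Rubin pooling. That is a fair reason for choosing Wald. Pooling did not remove the shortfall under the assumed models, but the plan's own rule could not be checked.
- **Newcombe has its own imbalance.** Its upper-side miss is above 2.5% in all 273 combinations, reaches 5.5%, and always exceeds its lower-side miss. This is true, although total coverage is restored and the remaining error is against the product. Miettinen-Nurminen is better balanced.
- **The extension to secondary endpoints is an inference.** SAP 2.4.4.1 speaks of the test and does not mention intervals, and the change history in SAP 2.9 makes the visits after optional treatment descriptive only. The point therefore applies there only so far as the intervals of SAP 2.4.3 are carried over.

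**Conclusion.** The concern holds. At the planned 282 v 47, the interval labelled 95% covers about 90-94% if the true control rate is 2-20%, and about 93-94% if it is 20-40%, given a true treated rate of 60-90%. The lower limit is too high more often than the upper limit is too low. The shortfall grows if mITT has fewer controls, and shrinks to about one point at control rates of 30-40%.

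The arithmetic is exact. Its relevance to this trial depends on response rates that the visible text does not give. The CMH test, the success rule, the point estimate and the sample size are unaffected. The sponsor should correct this, but it does not threaten the primary decision.

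Two matters cannot be judged from the visible text: the interval used for the needle and cannula comparisons (SAP 2.4.3.2), and how intervals are combined over imputations (Appendix H).

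**What to change.** In SAP 2.4.3, and in 2.4.4.1 where it follows 2.4.3:

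- **Single rates:** use Wilson. At n = 47 it covers 93.2-97.1% for true rates of 2-40%. With zero responders its upper limit is 3.84/(47 + 3.84) = 7.6%, so the interval does not collapse.
- **Difference:** use a score-based interval. Newcombe is simplest and keeps the SAP's simple difference as the point estimate. On the same 273 combinations it covers 94.5-96.0%, with a lower-side miss of at most 2.3%. Miettinen-Nurminen covers 94.9-96.7%, with misses of at most 2.4% (lower side) and 3.6% (upper side).
- **Stratification:** if the interval is stratified by injection tool with CMH weights, report the matching weighted difference as the point estimate.
- **Imputation:** state a combining rule consistent with Appendix H, which may already contain one.
- **Needle and cannula comparisons:** make the same change only if SAP 2.4.3.2 also uses Wald.

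The cost is SAP wording, programming and the check of the combining rule. Newcombe and Miettinen-Nurminen are not in estimate-plus-or-minus-SE form, so that check is real work. The reported lower limit falls by about 0.2-4.2 points with Miettinen-Nurminen or 0.2-5.1 with Newcombe (observed treated rate 60-90%, 0 to 19 of 47 control responders), least at high control rates. No new data are needed, and the test, success rule and sample size do not change.

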#### 2.4.4 Secondary analysis

All secondary endpoint analyses will be conducted using the ITT Population. In general, "by treatment group" refers to the Restylane-L Needle, Restylane-L Cannula, Restylane-L (pooled), and the No Treatment group.

#### 2.4.4.1 GIHS

Responder rates based on the GIHS determined by the Blinded Evaluator (described in Section 1.3.1) will be analyzed using the CMH test stratified by injection tool. This test will use the ITT Population on the observed cases following the methods described in Section 2.4.3 and will be presented by visit. No correction for multiplicity will be done; p-values (if generated) will only be provided for ease of interpretation of the results.

#### 2.4.4.2 GAIS

GAIS aesthetic improvement (overall appearance), as determined separately by the Treating Investigator and Subject, will be presented in frequency tables. The response rates (defined in Section 1.3.2) based on the GAIS as assessed by the Treating Investigator will be calculated and presented, separately, by treatment group. The actual GAIS ratings of the Treating Investigator will also be presented similarly and by visit.

The methods described above will be repeated for the GAIS results as determined by the Subject.

GAIS results, including both responder (Yes/No) and the actual GAIS ratings of the Treating Investigator and Subject, will be presented by treatment and subject in data listing.

MA-42205

Doc id

2022-08-17 17:26

Effective date: 2021-12-17 13:25

CCI		

43USTT1904 Statistical analysis plan - Tear Trough

#### Safety Analysis

All safety analyses will be performed based on the safety population set. In general, "by treatment group" refers to the Restylane-L Needle, Restylane-L Cannula, Restylane-L (pooled), and the No Treatment group.

### 2.5.1 Extent of exposure

### Injection Characteristics

Injection characteristics include, for each treatment (initial, touch-up, re-treatment), injection administration, procedural anesthetics, and post-injection concomitant procedures used. The

	Title 43USTT1904 Statistical analysis plan - Tear Trough	Doc id
GALDERMA		MA-42205

2022-08-17 17:26

following parameters will be summarized descriptively for the infraorbital hollows combined, for each treatment separately:

- Number of subjects treated
- Total number of syringes used
- Needle used (Co-pack, Other, Needle group only)
- Cannula used (25G x 1.5 in, 27G x 1.5 in; Cannula group only)
- Injection method (Linear antegrade, Linear retrograde, Fanning, Micro-bolus, Serial puncture, Other)
- Injection depth (Supraperiosteal, Other)

The following parameters will be summarized for each treatment separately, by treatment group:

- Procedural Anesthetics (No, Yes)
- Type of Anesthetics (Topical, Local Injection)
- Injection Concomitant Procedures (None, Massage, Ice Pack, Other)

If a subject receives more than one injection for a given treatment period, only the injection given closest to the protocol-specified injection visit (Appendix G) will be presented in the injection characteristics summary.

#### Injection Volume Administered

The injection volume (mL) administered throughout the study will be presented descriptively by the following timepoints, by group (where applicable):

- Initial treatment The amount of study product injected into subjects at the baseline visit (for subjects randomized to Restylane-L) or at the Month 12 visit (for subjects randomized to No Treatment).
- Optional Touch-up The amount of study product injected into subjects at the Month 1 visit. Only applicable to subjects randomized to Restylane-L.
- Initial treatment + Touch-up The cumulative sum of study product injected into subjects for the initial and touch-up treatments, regardless of how many treatments a subject received. This will be presented for both treatment groups.
- Re-Treatment The amount of study product injected into subjects at the Month 12 visit.
   Only applicable to subjects randomized to Restylane-L.
- Total injected volume The cumulative sum of study product injected into subjects across
  every potential injection timepoint, regardless of how many injections a subject got. This
  will be presented for both treatment groups.

If a subject receives more than one injection for a given treatment period, their total volume from all injections will be summarized in the 'Total injected volume' timepoint. Only the injection given closest to the protocol-specified injection visit (Appendix G) will be presented in each respective timepoint section described above.

All injection volume, injection characteristics, procedural anesthetics, and injection concomitant procedures data will be presented by treatment and subject in data listings.

#### 2.5.2 Adverse events

All AE data will be summarized by needle, cannula, and no treatment separately. Only AEs occurring after first injection, for subjects randomized to Restylane-L or after randomization for subjects randomized to No Treatment, or AEs that worsened, will be included in analysis. AEs occurring before, if any, will only be listed in subject data listings.

	Title 43USTT1904 Statistical analysis plan - Tear Trough	Doc id
GALDERMA		MA-42205

2022-08-17 17:26

All AE endpoints will be presented by the timepoint in which they occurred, defined as:

- No Treatment at Baseline: For subjects randomized to No Treatment, an AE which starts between date of randomization up until the time of their first injection.
- Initial Treatment with Restylane-L: For subjects randomized to Restylane-L, an AE which starts on or after their baseline injection up until their optional retreatment (including optional touch-up); for subjects randomized to No Treatment, an AE which starts on or after their optional initial treatment.
- Retreatment with Restylane-L: For subjects randomized to Restylane-L, an AE which starts on or after their optional retreatment.

Missing dates, severity, relationship, and seriousness will be imputed as described in Section 2.4.2. Adverse Events will be summarized by SOC and PT. The MedDRA version used for the coding will be noted as a footnote in the tables and listings.

A summary of AEs will be provided, which will include the number and percentage of subjects and number of events with the following categories of:

- Any AE
- Any Serious AE
- Any AE related to study product or injection procedure
- Any Serious AE related to study product or injection procedure
- Any AE unrelated to study product or injection procedure
- · Any Serious AE unrelated to study product or injection procedure
- Any AESI
- Any Serious AESI
- Number of subjects who did not have an AE

Summaries of related AEs (including the total number of events, number and percentage of subjects) will be displayed by treatment grouping specified above according to the following:

- All AEs related to study product or injection procedure by SOC, PT, and maximum intensity (mild, moderate, or severe)
- All AEs related to study product or injection procedure by SOC, PT, and duration of event
- All AEs related to study product or injection procedure by SOC, PT, and number of days to onset of event
- All AEs by SOC, PT, and action taken (none, medical treatment, non-pharmacological treatment, subject withdrawn)
- All AEs unrelated to study product or injection procedure by SOC, PT, and maximum intensity (mild, moderate, or severe)

For the subject level analyses, the number and percentage of subjects who experienced at least one of the events listed above will be summarized overall and for each SOC and each PT. System organ class and PTs will be presented in descending frequency first (by treatment group), and then alphabetically if there are ties. Each subject will contribute at most one count per summarization category. In other words, if a subject has more than one AE with same PT, the subject will be counted only once for that PT. Similarly, if a subject has more than one AE for a SOC, the subject will be counted only once in that SOC and PT. For the event level analyses, the counts of each respective event will be presented. In general, percentages) will be calculated using the number of subjects in the Safety population for the denominator.

[figure not shown]
2022-08-17 17:26

For the "action taken" summary specifically, subjects will be only counted in 'None' category if no other action was taken. For the onset/duration summaries, number of days to onset and duration of event will be summarized by SOC and PT, using mean, SD, minimum, maximum, and median statistics. Time to onset of an AE will be derived as the start date minus the date of most recent treatment. Duration of an AE will be derived as the stop date minus the start date + 1. Imputation rules for partial/completely missing dates are specified below. Missing stop date will not be imputed and therefore no duration will be calculated in these cases. Instead, the number of AEs that were ongoing at the end of the study will be given.

All reported AEs will be listed in data listings including time to onset, duration of AE, action taken (if applicable) and severity. By-subject listings also will be provided for all subjects for the following: Pre-treatment and AEs, AE severity, AEs related to study product or injection procedure, serious adverse events (SAEs), AEs leading to discontinuation of study drug, action taken, and resolution or outcome.

